13.7. Appendix 7: Reporting Standards for Missing Data

13.7.1. Premature Withdrawals

Element	Reporting Detail
General	
 Participant study completion (i.e. as specified in the protocol) was defined as a participant who has completed all phases of the study including the follow-up visit. Withdrawn participants may be replaced in the study. All available data from participants who were withdrawn from the study will be listed and all available planned data will be included in summary tables and figures, unless otherwise specified.
Outliers	
 Any participants excluded from the summaries and/or statistical analyses will be documented along with the reason for exclusion in the clinical study report.

13.7.2. Handling of Missing Data

Element	Reporting Detail
General	
 Missing data occurs when any requested data is not provided, leading to blank fields on the collection instrument: 
 These data will be indicated by the use of a “blank” in participant listing displays. Unless all data for a specific visit are missing in which case the data is excluded from the table. Answers such as “Not applicable” and “Not evaluable” are not considered to be missing data and should be displayed as such.
Exposure	
 If study treatment stop date is missing, then for the purposes of calculating exposure, it will be imputed using the date of last visit or the recorded date of withdrawal/completion whichever is earlier. Partially Missing Stop Day: Last day of the month or last month of the year will be used, unless this is after the date of last visit or the recorded date of withdrawal/completion; in this case the earliest of the two dates will be used.
Outliers	
 Any participants excluded from the summaries and/or statistical analyses will be documented along with the reason for exclusion in the clinical study report.

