A qualified participant will be randomized into the treatment phase of the study and will administer study treatments, once daily, from Day 1 through Day 10 in Part 1 and from Day 1 through Day 7 in Part 2. On Day 1, an appropriate number of bottles will be dispensed, with a supply sufficient to cover the entire treatment period. The blinded bottles will contain capsules of either the active dose or placebo. Dosing instructions will be indicated on each bottle. Participants will bring the bottles of study treatments to each visit, so that study treatment can be administered in the clinic after the study procedures have been performed.

Each dose of study medication will be taken with approximately 240 mL (8 ounces) of water following ingestion of a moderate calorie and fat meal (i.e. at least 400 calories, with at least 120 calories from fat), that is required to be completed within 30 minutes prior to dosing. A moderate calorie and fat breakfast is planned to be similar to the following (additional meal suggestions will be included in the Study Reference Manual [SRM]):

- 2 slices of bread
- 10 g of butter
- 20 g of jam
- 15 g of cheese
- 175 mL of apple juice

Study treatments should be administered near the same time each morning, within a 2-hr window.

On days when the participant self-administers the study treatments, observed dosing with a site staff member may be achieved as locally permitted using various forms of video calling (when at all possible) such as FaceTime, Skype, WhatsApp.

Participants will then enter the post-dosing period:

Study Part 1:

There are 4 in-clinic visits in the Part 1 post-dosing period: 3 visits for PK and other assessments during the 7 days immediately following the last dose, and a final follow-up visit primarily for safety (e.g., to follow any AEs to resolution) approximately 8-14 days after the last dose, as shown in the Part 1 Schedule of Activities (SOA, Section 2). In Part 1, participants should not start other medicines and will not start ARVs during the post-dosing period until they have completed the final follow-up visit.

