In the shortest course for Part 1, a participant can be screened/qualified, treated and assessed for all the planned visits (including the final follow-up visit) in approximately 30 days (if, for example, only 10-14 days are needed for the screening period and the final follow-up visit is performed on Day 18). In the longest course for Part 1, a participant can be screened/qualified, treated and assessed for all the planned visits (including the final follow-up visit) in 52 days (if, for example, 28 days are needed for the screening period and the final follow-up visit is performed on Day 24).

Study Part 2:

There are 2 in-clinic visits in the Part 2 post-dosing period: 1 visit for PK and other assessments on the day immediately following the last dose, and a final follow-up visit primarily for safety (e.g., to follow any AEs to resolution) 3-5 days after the last dose, as shown in the Part 2 Schedule of Activities (SOA, Section 2).

In Part 2, participants will start Investigator-selected, prescribed and provided cART immediately following the completion of the primary endpoint, i.e., the measurement of HIV-1 RNA on Day 8.

In the shortest course for Part 2, a participant can be screened/qualified, treated and assessed for all the planned visits (including the final follow up visit) in approximately 24 days (if, for example, only 10-14 days are needed for the screening period and the final follow-up visit is performed on Day 10). In the longest course, a participant can be screened/qualified, treated and assessed for all the planned visits (including the final follow-up visit) in 40 days (if, for example, 28 days are needed for the screening period and the final follow-up visit is performed on Day 12).

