6.2.6. Exposure and Treatment Compliance

The complete dosing experience will be listed for all participants. The total duration of exposure (number of days on study drug), average daily dose, and cumulative dose will be summarized by treatment group.

CONFIDENTIAL

208132

For participants who completed the 10-day treatment period in Part 1 and 7-day treatment period in Part 2 of the study, the expected number of doses is 10 for Part 1 and 7 for Part 2. For participants who permanently discontinued the study treatment and/or withdrew from the study, the expected number of doses during the treatment period will be calculated using “Days on study drug” where “Days on study drug” is Last Dose Date – First Dose Date +1.

A summary of study medication compliance will be produced by treatment group: >0- <100%, 100%, >100%. The compliance will be calculated for the whole study treatment period as the percentage of cumulative dose [$100 * (\text{actual cumulative dose}) / (\text{expected cumulative dose for the participant's treatment duration})$].

For participants who completed the 10-day treatment period in Part 1 or 7-day treatment period in Part 2, the expected cumulative dose of GSK3640254 taken during the treatment period would be planned dose*10 days or planned dose*7 days. E.g. For participants who received 200 mg GSK3640254 in Part 1, the expected cumulative dose is 2,000 mg GSK3640254 (the 200 mg of IP is comprised of two 100 mg capsules of GSK3640254 administered daily over the 10-day treatment period).

For participants who permanently discontinued study treatment or withdrew early from the study, the expected cumulative dose of GSK3640254 taken during the treatment period would be the planned dose*(Last Dose Date – First Dose Date + 1).

The actual cumulative dose of GSK3640254 for all participants is the sum of all doses, in mg, of study drug consumed for the duration of the study. (Approach for handling missing treatment stopping dates is discussed in Section [13.7.2](#))

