13.4. Appendix 4: Study Phases and Treatment Emergent Adverse Events**13.4.1. Study Phases**

Assessments and events will be classified according to the time of occurrence relative to the start and/or stop date of the study treatment.

Study Phase	Definition
Screening Period	Day -28 to Day -1
Treatment Period	Day 1 to Day 10 / study treatment stop date in Part 1 and Day 1 to Day 7 / study treatment stop date in Part 2
Follow-up Period	Study treatment stop date + 1 to Day 24 in Part 1 and study treatment stop date + 1 to Day 12 in Part 2

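### A missing treatment stop date is imputed from visit or completion dates with no cap at the last dosing day, which overstates exposure duration for participants who complete dosing

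*SAP*

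**What the plan says.** SAP Section 13.7.2 (Exposure row) covers a missing study treatment stop date. For exposure calculations only, "it will be imputed using the date of last visit or the recorded date of withdrawal/completion whichever is earlier". A partly missing stop date is moved to the end of the month or year, limited only by the same two dates. Section 6.2.6 relies on this rule: "Approach for handling missing treatment stopping dates is discussed in Section" 13.7.2.

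Section 6.2.6 summarises duration of exposure, average daily dose and cumulative dose by treatment group. It defines days on study drug as last dose date minus first dose date plus 1. For participants who completed treatment, "the expected number of doses is 10 for Part 1 and 7 for Part 2", and the expected cumulative dose is the planned dose times 10 or times 7. Only for those who discontinued or withdrew does the expected dose use the last dose date.

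Dosing ends by design on Day 10 (Part 1) or Day 7 (Part 2). The protocol synopsis puts the final follow-up visit "approximately 8-14 days after the last dose" in Part 1 and "3-5 days after the last dose" in Part 2. SAP Section 13.7.1 counts a participant as having completed the study only once the follow-up visit is done.

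**The concern.** Neither date in the rule is tied to dosing. Follow-up runs beyond dosing in both parts, and for a participant who completes the study both dates belong to the end of follow-up. Taking the earlier of two dates that are both too late gives no protection.

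The result also sits badly with the SAP's own study phases. Section 13.4.1 defines the treatment period as "Day 1 to Day 10 / study treatment stop date in Part 1 and Day 1 to Day 7 / study treatment stop date in Part 2". The days after that belong to follow-up, given for Part 1 as "Study treatment stop date + 1 to Day 24 in Part 1" and, for the second part, as "study treatment stop date + 1 to Day 12 in Part 2". The imputation would count follow-up days as days on study drug. In Part 2 these include days on combination antiretroviral therapy, which starts on Day 8.

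The outputs at stake are Table 1.19 (exposure, a headline deliverable) and, for early stoppers only, Table 1.18 (compliance). Cohorts have 6 participants, so one bad date is visible in a mean.

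**Working it through.** **Inputs.** Last planned dose: Day 10 or Day 7 (protocol synopsis; SAP 6.2.6). Final visit: Day 18-24 or Day 10-12 (protocol Section 2.2). Follow-up visit after withdrawal: 7-14 days (Part 1) or 3-5 days (Part 2) after treatment stopped (protocol Section 8.2). Cohort size: 6 (protocol Section 5.2).

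**The SAP's own figure.** Expected cumulative dose for a 200 mg completer in Part 1 is 200 × 10 = 2,000 mg, as stated in Section 6.2.6.

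**Duration, dosing completer who attends the final visit.** Day 1 is the first dose, so imputed duration equals the final visit day. Overstatement = final visit day / last dosing day − 1.

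| | Lag (days) | Imputed | True | Overstatement |
|---|---|---|---|---|
| Part 1, earliest | 18 − 10 = 8 | 18 | 10 | +80% |
| Part 1, latest | 24 − 10 = 14 | 24 | 10 | +140% |
| Part 2, earliest | 10 − 7 = 3 | 10 | 7 | +43% |
| Part 2, latest | 12 − 7 = 5 | 12 | 7 | +71% |

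If such a participant's last visit was instead Visit 6 (Day 11 or Day 8), the excess is 1 day: 11/10 gives +10% and 8/7 gives +14%.

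**Effect on a cohort mean, one of six affected.**
- Part 1: (5 × 10 + 18)/6 = 11.3 and (5 × 10 + 24)/6 = 12.3 days.
- Part 2: (5 × 7 + 10)/6 = 7.5 and (5 × 7 + 12)/6 = 7.8 days.
- If the other five each have the planned duration, the median does not change.

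**Average daily dose, assuming cumulative dose / duration.**
- One participant at 200 mg: 2,000/18 = 111 and 2,000/24 = 83 mg/day.
- One participant at 140 mg: 980/10 = 98 and 980/12 = 82 mg/day.
- Mean of the 140 mg arm with one affected: (5 × 140 + 98)/6 = 133 and (5 × 140 + 81.7)/6 = 130 mg/day.

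**Compliance.** For a treatment completer it is 10/10 or 7/7 = 100% whatever the stop date. For a participant who discontinued or withdrew, the denominator uses the last dose date. Take three doses, all taken as planned, so that true compliance is 100%:
- Withdrawal recorded on the day of the last dose: 3/3 = 100%, no error.
- Withdrawal and last visit both dated at the follow-up visit: Part 1, 3/(3 + 7) = 30% to 3/(3 + 14) = 18%; Part 2, 3/(3 + 3) = 50% to 3/(3 + 5) = 38%.

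**Partial dates.** The error varies. If the last dose is on the 30th of a 31-day month and follow-up falls in the next month, month end gives an error of 1 day.

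**The case against.** The strongest objection is that the rule will hardly ever be used. Dosing is observed or checked by contact every day, protocol Section 7.6 sends treatment start and stop dates to the CRF, and the data are cleaned before release. A 12-day exposure in a 7-day part would also stand out. This is fair and keeps the point minor. It does not make the rule correct when it is used.

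Three stronger readings are tempting, and the documents do not support them.

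- **A reader might infer that compliance is understated generally.** It is not. SAP 6.2.6 fixes the completer's denominator at the planned dose times 10 or 7, so no stop date enters.
- **A reader might infer that the rule is wrong every time it is applied.** It takes the earlier date, and protocol Section 8.1.4 says that stopping study treatment requires withdrawal from the study. An early stopper's withdrawal date can therefore equal the stop date, with zero error. It can also be later: protocol Appendix 7 describes permanently stopping treatment after a liver event while staying in the study for follow-up. The documents do not settle which date would be recorded, so no single error range applies to early stoppers.
- **A reader might infer that a 140 mg arm would look like the 80 mg arm, or that safety results would be distorted.** The 82-98 mg/day figure is for one participant; the arm mean would be about 130-133 mg/day, and only under the assumed formula. Cumulative dose is the sum of doses taken and does not change. Safety is analysed by treatment received. The imputation is confined to exposure, and the treatment-emergent flag in SAP 13.4.2 runs to the final follow-up visit in any case.

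**Conclusion.** The rule is wrong as written, and the consequence is minor. It has no cap at the last dosing day. For a dosing completer who attends the final visit it gives 18-24 days instead of 10, or 10-12 instead of 7. That is an overstatement of 80-140% in Part 1 and 43-71% in Part 2.

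This rests on three assumptions: the completion date is that of the follow-up visit, as SAP 13.7.1 implies; the imputed stop date serves as the last dose date; and the duration formula in Section 6.2.6 applies to completers as well as early stoppers.

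Lower average daily dose follows only if it is calculated as cumulative dose over duration. For participants who discontinued or withdrew, duration is overstated and compliance understated only when the recorded withdrawal date and the last visit both fall after the last dose. The partial-date rule lacks the same cap, but its error can be small. The documents give no expected number of missing stop dates, and the daily dosing checks suggest few.

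**What to change.** Replace the missing-date and partial-date rules in the Exposure row of SAP 13.7.2 with: *A missing or partial study treatment stop date is imputed as the date of the last documented dose in the daily dosing record. If there is none, the earliest of the planned last dosing day of that part (Day 10 or Day 7), the recorded discontinuation or withdrawal date and the last visit date is used.*

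The documented dose must come first. Taking the earliest of all the dates would discard a documented dose taken after Day 10 or Day 7 and hide extra exposure.

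With this rule, a completer with a missing date who dosed as planned returns to 10 or 7 days (overstatement 0%), and completer compliance stays at 100%. The cost is one replacement passage in the SAP and the matching line of derivation code. The dosing record is already collected daily, so no new data are needed and nothing changes in study conduct. Stating the average daily dose formula in Section 6.2.6 at the same time would remove the one conditional part of this point.

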13.7.2.1. Handling of Missing and Partial Dates

Element	Reporting Detail
General	
 Partial dates will be displayed as captured in participant listing displays.
Adverse Events	
 The eCRF allows for the possibility of partial dates (i.e., only month and year) to be recorded for AE start and end dates; that is, the day of the month may be missing. In such a case, the following conventions will be applied for calculating the time to onset and the duration of the event: 
 Missing Start Day: First of the month will be used unless this is before the start date of study treatment; in this case the study treatment start date will be used and hence the event is considered On-treatment as per Appendix 4: Study Phases and Treatment Emergent Adverse Events. Missing Stop Day: Last day of the month will be used, unless this is after the stop date of study treatment; in this case the study treatment stop date will be used. Completely missing start or end dates will remain missing, with no imputation applied.

CONFIDENTIAL

208132

Element	Reporting Detail
	Consequently, time to onset and duration of such events will be missing.
Concomitant Medications/ Medical History	
● Partial dates for any concomitant medications recorded in the CRF will be imputed using the following convention:
○ If the partial date is a start date, a '01' will be used for the day and 'Jan' will be used for the month○ If the partial date is a stop date, a '28/29/30/31' will be used for the day (dependent on the month and year) and 'Dec' will be used for the month.● The recorded partial date will be displayed in listings.

CONFIDENTIAL

208132

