2. SCHEDULE OF ACTIVITIES (SOA)

2.1. Part 1 and Part 2 Screening

Procedure ¹	Screening (14 days ² before Day 1)	Notes
Clinical Assessments		
Outpatient Visit	X	
Informed Consent	X	
Medical/medication/drug/alcohol history	X	
Prior anti-retroviral therapy	X	
Serious Adverse events (SAE) Assessment	X	Section 9.2
Center for Disease Control and Prevention (CDC) Classification	X	
Human immunodeficiency virus (HIV)-associated conditions assessment	X	
Height, Weight, Body Mass Index (BMI)	X	Section 9.4.1
Vital Signs	X	Section 9.4.2
Columbia Suicide Severity Rating Scale (C-SSRS) administration – Baseline form	X	Section 9.4.5
Clinical Procedures		
Electrocardiogram (ECG) (single reading)	X	Section 9.4.3
Pregnancy Test (Urine or Serum Human chorionic gonadotropin [β -hCG])	X	Section 9.2.6
Hematology/Chemistry/Urine	X	Section 9.4.4
Fasting Lipid Panel (approximately 8 hours)	X	Section 9.4.4
Hepatitis B Virus (HBV) and Hepatitis C Virus (HCV) serologies ³	X	
Lymphocyte T-cell subsets (Cluster of designation 4 [CD4], CD8)	X	Section 9.1.2
HIV-1 Ribonucleic Acid (RNA)	X	Section 9.1.1
Drugs of Abuse	X	
Interactive Web Response System (IWRS) (RAMOS) activity ⁴	X	

1. Procedures should be performed in this order: 1: ECG, Vital Signs, Blood Draws
2. Participants will be randomized within 14 days of the start of Screening; up to 28 days maximum may be allowed in some cases.
3. If test was otherwise performed within 3 months prior to first dose of study treatment, testing at Screening is not required.
4. Log in to RAMOS to complete a registration for participant ID assignment. If the participant fails screening, log in to RAMOS to register the participant as a Screen Fail.

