9.2.1. Time Period and Frequency for Collecting AE and SAE Information

- All SAEs will be collected from the signing of the ICF until the final follow-up visit at the time points specified in the SOA (Section 2).
- All AEs will be collected from the start of treatment until the final follow-up visit at the time points specified in the SOA (Section 2).
- Medical occurrences that begin before the start of study treatment but after obtaining informed consent will be recorded on the Medical History/Current Medical Conditions section of the case report form (CRF) not the AE section.
- All SAEs will be recorded and reported to the sponsor or designee immediately and under no circumstance should this exceed 24 hours, as indicated in [Appendix 4](#). The investigator will submit any updated SAE data to the sponsor within 24 hours of it being available.
- Investigators are not obligated to actively seek AEs or SAEs in former study participants. However, if the investigator learns of any SAE, including a death, at any time after a participant has been discharged from the study, and he/she considers the event to be reasonably related to the study treatment or study participation, the investigator must promptly notify the sponsor.
- The method of recording, evaluating, and assessing causality of AEs and SAEs and the procedures for completing and transmitting SAE reports are provided in [Appendix 4](#).

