13.4.2. Treatment Emergent Flag for Adverse Events

Flag	Definition
Treatment Emergent	Study Treatment Start Date ≤ AE Start Date ≤ Final Follow-up Visit.

NOTES:

- If the study treatment stop date is missing, then the AE will be considered to be On-Treatment.
- Time of study treatment dosing and start/stop time of AEs should be considered, if collected.

CONFIDENTIAL

208132

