13.6. Appendix 6: Derived and Transformed Data

13.6.1. General

Multiple Measurements at One Analysis Time Point

 • Mean of the measurements will be calculated and used in any derivation of summary statistics but if listed, all data will be presented. • Triplicate 12-lead ECGs will be recorded at each study-specified visit. Mean of the measurements will be calculated and used in any derivation of summary statistics but if listed, all data will be presented. • Participants having both High and Low values for Normal Ranges at any post-baseline visit for safety parameters will be counted in both the High and Low categories of “Any visit post-baseline” row of related summary tables. This will also be applicable to relevant Potential Clinical Importance summary tables.
Study Day

 • Calculated as the number of days from First Dose Date: 
 • Ref Date = Missing → Study Day = Missing • Ref Date < First Dose Date → Study Day = Ref Date – First Dose Date • Ref Date ≥ First Dose Date → Study Day = Ref Date – (First Dose Date) + 1

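### The SAP's rule for a missing AE start day moves a screening SAE to Day 1 and flags it on-treatment, even when its recorded month or end date shows it began before the first dose

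*SAP*

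**What the plan says.** SAP 13.7.2.1 covers records where the day is missing but month and year are known: "The eCRF allows for the possibility of partial dates (i.e., only month and year) to be recorded for AE start and end dates". The rule for a missing start day reads: "First of the month will be used unless this is before the start date of study treatment; in this case the study treatment start date". The SAP goes on to spell out what status such a record receives: the substituted date "will be used and hence the event is considered On-treatment as per Appendix 4". A missing stop day has its own rule: "Last day of the month will be used, unless this is after the stop date of study treatment". Imputed stops are thus capped at the end of dosing. Neither rule compares the imputed start with the end date.

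SAP 13.4.2 defines treatment-emergent as "Study Treatment Start Date ≤ AE Start Date ≤ Final Follow-up Visit". SAP 13.6.1 makes an event dated on the first dose Study Day 1: "Ref Date ≥ First Dose Date → Study Day = Ref Date – (First Dose Date) + 1".

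On what the AE data can contain, Protocol 9.2.1 states: "All SAEs will be collected from the signing of the ICF until the final follow-up visit". The screening schedule in Protocol 2.1 includes a line for "Serious Adverse events (SAE) Assessment", and SAP 13.4.1 runs the screening period from Day -28 to Day -1. Non-serious AEs are collected only from the start of treatment.

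**The concern.** Using the first-dose date is a sensible cautious convention when the event could have begun before or after dosing, that is, when the recorded month is the dosing month and nothing else settles the order. As written, the condition is wider. The first of the month precedes the first dose for every earlier month as well, and there the timing is not ambiguous: the record already shows onset before treatment. The same applies in the dosing month when the end date is known and falls before the first dose.

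In those cases the derivation contradicts collected data. At stake is whether a pre-treatment SAE carries a Day 1 onset and an on-treatment flag in a study with cohorts of 6 active and 2 placebo participants. Sponsor staff may see unblinded data, so this rule is better corrected in the SAP than case by case at reporting.

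**Working it through.** The SAP states no figure here to reproduce, so the check applies the rule literally.

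**Inputs.** Start-day rule (SAP 13.7.2.1); flag (SAP 13.4.2); study-day formula (SAP 13.6.1); screening up to 28 days (SAP 13.4.1); SAE collection from consent (Protocol 9.2.1). The SAP gives no formula for AE duration; end minus start plus 1 is assumed.

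**Rule in symbols.** Let F be the first-dose date and M1 the first of the recorded month. If M1 < F, start = F; otherwise start = M1.

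**Example 1, earlier month.** F = 5 April; SAE start recorded as March, day missing; end 20 March.
- M1 = 1 March < 5 April, so start = 5 April.
- Study day = 5 April - 5 April + 1 = 1, so the event is treatment-emergent.
- Duration = 20 March - 5 April + 1 = -16 + 1 = -15 days.
- If the end day is also missing, the stop rule gives 31 March and the duration is -5 + 1 = -4 days.

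**Example 2, dosing month with a known end.** F = 5 April; start recorded as April, day missing; end 3 April.
- M1 = 1 April < 5 April, so start = 5 April, Study Day 1, treatment-emergent.
- Duration = 3 April - 5 April + 1 = -2 + 1 = -1 day.

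**How often screening reaches an earlier month.** Assume a uniform first-dose date over a 365-day year and uniform onset over the screening days. Day -k falls in an earlier calendar month for k first-dose dates in each of 12 months.
- 28-day screening: 12 × (1 + … + 28) / (365 × 28) = 12 × 406 / 10,220 = 4,872 / 10,220 = 47.7%.
- 14-day screening: 12 × (1 + … + 14) / (365 × 14) = 12 × 105 / 5,110 = 1,260 / 5,110 = 24.7%.

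These shares are conditional on a screening SAE with a missing start day. Under the rule as written, 100% of such events are flagged treatment-emergent. With the substitution limited to the dosing month, the share falls to 52.3% (28 days) or 75.3% (14 days), before any end-date check.

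**Corrected rule on the same examples.**
- Example 1: start = 1 March; study day = 1 March - 5 April = -35; pre-treatment; duration = 20 - 1 + 1 = 20 days.
- Example 2: start = 1 April; study day = 1 April - 5 April = -4; pre-treatment; duration = 3 - 1 + 1 = 3 days.

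**The case against.** The strongest reply is that this changes nothing a reader of the summary tables would see. SAP 8.1 and Tables 3.1 to 3.10 describe all, drug-related, serious, special-interest and discontinuation events, and none of those titles is limited to treatment-emergent events. That wording appears in table titles only for laboratory and liver toxicities. No summary-table title names time to onset or duration, and listings show partial dates as captured, so the true month stays visible. All of this stands, and it limits the consequence.

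Cases will also be very few. The event must be an SAE during screening, in someone still judged healthy apart from HIV and then dosed, with an unknown start day despite 24-hour reporting and source verification. That stands too.

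Two textual defences are weaker. Protocol 9.2.1 sends medical occurrences between consent and first dose to Medical History and states no exception for serious ones, but the same section collects all SAEs from consent, and the screening schedule assesses them. SAP 13.4.2 asks that dosing time and AE start and stop times be considered if collected. This may mean clock time, and it does not clearly override the explicit imputation rule.

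Finally, the error is cautious in direction, since it attributes an event to treatment rather than hiding one. Caution is a reason for the convention when order is unknown; it does not justify overriding a recorded month or end date.

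**Conclusion.** The point holds as a minor one: a stated rule gives a wrong result for a definable set of records. For a screening SAE with a missing start day, whose recorded month precedes the dosing month or whose known end date precedes the first dose, the flag, study day and time to onset are wrong. Duration is negative only if the event ended before the first dose; for an event that continued past dosing it is shortened, not negative.

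A reader might infer that one such case adds 1/6 = 16.7 percentage points to the SAE rate of an active arm, or 1/2 = 50 points in a placebo arm. The documents do not support that. On the listed titles, a screening SAE held in the AE data would be counted in the SAE table with or without the imputation. The shift would arise only in an output filtered on the flag, and none of the listed AE or SAE tables is expressly so filtered.

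The 47.7% and 24.7% shares rest on uniform dates and are conditional on an event whose frequency the documents do not give. They show that crossing a month boundary is ordinary, not that cases are common.

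**What to change.** Reword the missing-start-day rule in SAP 13.7.2.1 as follows:

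- Use the first-dose date only when the recorded month and year equal those of the first dose and any recorded end date is not before the first dose.
- In all other cases (earlier month, later month, or dosing month with an end date before the first dose), impute the first of the recorded month.
- Derive the treatment-emergent flag in SAP 13.4.2 from the resulting date, so that an onset before the first dose is pre-treatment.

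This supplies a start date in every case and keeps the cautious convention where the order is truly unknown. The imputed first of the month can fall before consent (Day -35 in Example 1); that does not affect the flag, but onset day and duration for such records remain conventions. The cost is a few lines of SAP text and date-imputation code, with no new data.

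### A missing adverse-event stop day is capped at the last dose, so derived duration is impossible or too short for events that start or resolve in follow-up

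*SAP*

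**What the plan says.** SAP Section 13.7.2.1 explains that the eCRF accepts AE dates with only month and year, and sets conventions "for calculating the time to onset and the duration of the event". For the stop date the rule is to take the end of the month, "unless this is after the stop date of study treatment; in this case the study treatment stop date will be used". The rule has no condition linking the imputed stop to the AE start. The same section leaves completely missing dates unimputed and shows partial dates in listings as they were recorded.

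The period over which AEs count is longer than the treatment period. Protocol Section 9.2.1 states: "All AEs will be collected from the start of treatment until the final follow-up visit". SAP Section 13.4.2 defines treatment-emergent as "Study Treatment Start Date ≤ AE Start Date ≤ Final Follow-up Visit". SAP Section 13.4.1 gives the Part 1 treatment period as "Day 1 to Day 10 / study treatment stop date in Part 1" and the Part 1 follow-up period as "Study treatment stop date + 1 to Day 24 in Part 1". The matching days for Part 2 are Day 7 for the end of treatment and Day 12 for the end of follow-up.

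**The concern.** The stop-day rule treats the last dose as the latest date on which an AE can end, while the rest of the plan expects AEs to start and resolve after it. Two things follow for an AE with a known start date and a partial stop date. If it starts in follow-up, its imputed stop comes before its onset. If it starts on treatment and resolves in follow-up, its duration is cut off at the last dose.

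What is at stake is the correctness of AE duration, a variable the SAP says it will calculate. For events that start on treatment and outlast it, the error runs in one direction, towards shorter events.

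**Working it through.** The documents give no figure to reproduce, so the check applies the rule as written.

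**Inputs.** Last dose T = Day 10 (Part 1) or Day 7 (Part 2), and latest follow-up day F = Day 24 or Day 12, all from SAP 13.4.1. The AE start S is known, the true stop is E, and only the month and year of E are recorded.

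**Rule.** Imputed stop = the earlier of (end of the month containing E) and T. Duration = stop - start + 1.

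**Why the cap always applies to these events.** If E is after T, the end of E's month is on or after E and so also after T. The imputed stop is then always T.

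**Onset after the last dose (S > T).** Duration = T - S + 1, which is zero or negative.
- Part 1, onset Day 20: 10 - 20 + 1 = -9 days.
- Part 1, onset Day 24 (worst case): 10 - 24 + 1 = -13 days.
- Part 2, onset Day 12 (worst case): 7 - 12 + 1 = -4 days.

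**Onset on treatment, resolution after the last dose.** The duration loses E - T days.
- Part 1, Day 8 to Day 24: true 24 - 8 + 1 = 17; imputed 10 - 8 + 1 = 3.
- Part 2, Day 6 to Day 11: true 11 - 6 + 1 = 6; imputed 7 - 6 + 1 = 2.
- Largest loss: 24 - 10 = 14 days in Part 1 and 12 - 7 = 5 days in Part 2.

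**Enumeration.** The rule was run over 365 first-dose dates and every start/stop pair up to F.
- Follow-up onset, Part 1: 14 x 15 / 2 = 105 pairs, x 365 = 38,325 combinations. The imputed stop precedes the start in all of them.
- Follow-up onset, Part 2: 5 x 6 / 2 = 15 pairs, x 365 = 5,475. The same holds in all of them.
- On-treatment onset with follow-up resolution: 10 x 14 x 365 = 51,100 (Part 1) and 7 x 5 x 365 = 12,775 (Part 2). All are shortened.
- Imputed stop in a different month from the one recorded: 24,780 of 89,425 (28%) in Part 1 and 1,920 of 18,250 (11%) in Part 2, among combinations that end in follow-up.

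These are counts over a grid. They show that the failure is systematic once a stop day is missing; they say nothing about how often stop days will be missing.

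**After moving the cap to F.** Stops before onset fall to 0 of 38,325 and 0 of 5,475. The new value is an upper bound. With first dose on the 4th of a 31-day month, a Part 1 event from Day 14 to Day 16 gets 24 - 14 + 1 = 11 days (true 3, current rule -3). One from Day 9 to Day 20 gets 24 - 9 + 1 = 16 (true 12, current rule 2).

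**The case against.** The case for leaving this alone is that little rests on it.

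- No listed AE table (3.1 to 3.10) summarises duration or time to resolution. They report counts by term, grade, relatedness, seriousness and discontinuation. At most, duration could appear as a derived field in AE listings, whose layouts are not in the text available. This stands.
- The trigger should be uncommon. AEs are assessed on every treatment day, including virtual days, and at each follow-up visit. Neither document gives a frequency for partial stop dates, so the number affected among about 34 participants is unknown. This also stands.
- For an AE that did resolve on treatment, the last dose is a valid upper bound. The cap also does nothing when the recorded stop month ends before the last dose. Both are true, but neither helps an event that ended later.
- A cap at the final follow-up visit alone would not be enough. Protocol Section 9.2.3 follows SAEs and AEs of special interest until they resolve or stabilise, which may be after that visit. This is right, and the fix allows for it.

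A reader might also infer that events still ongoing at study end are shortened. They are not: an AE with no end date is left missing. Nor does the defect undermine a planned assessment of gastrointestinal persistence. Protocol Section 3.3 states an expectation that preclinical-type GI findings would not persist after dosing, but no objective, endpoint or planned analysis uses AE duration to test it.

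**Conclusion.** The rule is wrong as written, and nothing elsewhere in the protocol or SAP corrects it. With a known start date and a missing stop day, every AE that starts after the last dose gets a duration of zero or less, down to -13 days in Part 1 and -4 in Part 2. Every AE that starts on treatment and resolves in follow-up is shortened, by up to 14 or 5 days. These figures assume dosing through Day 10 or Day 7 and follow-up to Day 24 or Day 12. If the start day is missing too, a stop before the start arises only when the AE start month is later than the month of the last dose.

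The consequence is minor. Only derived duration is affected. AE counts and the treatment-emergent flag depend on the start date, and listings keep the recorded partial dates, so the documents do not support reading this as a threat to the safety tables.

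**What to change.** Replace the stop-day sentence in SAP 13.7.2.1 with a rule of this form: impute the last day of the recorded month, capped at the date of last contact (final follow-up visit, withdrawal or completion, or later AE follow-up if any), never before the AE start date and never outside the recorded stop month.

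The SAP already uses a similar pattern. The exposure rule in Section 13.7.2 limits a partial stop date by the last visit or the withdrawal/completion date.

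The cost is one SAP sentence and the matching line in the derivation program, with no new data and no protocol change. The trade-off is that the imputed duration becomes an upper bound, including for events that really ended on treatment, so any display of it should mark the value as imputed.
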